#### *Data Storage and Confidentiality*

Only de-identified or non-identifiable data will be reported in the study. Only the research investigators and study staff will have access to patient information. All resulting data will be stored in electronic format; files will be stored on a password-protected computer and stored in a secured facility with limited access. Participants will not be excluded on socioeconomic, racial or religious identity. No form of deception will be used. The data collection and storage processes will follow HIPAA guidelines, in accordance with 21 CFR 46.115 (b); to protect both confidentiality and privacy of each participant. All PHI data will be erased or destroyed per institution protocol.

#### *Study Variables:*

The data to be collected from this study will include:

- Demographic (age, sex)
- Treatment group (normal saline/hypertonic saline)
- Modified Borg Scale Score (pre and post treatment)
- prn albuterol use
- 30 day readmission
- 30 day all cause mortality
- Spirometry data within 30 days

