## Methods

### *Study Population:*

This study will involve 146 patients admitted to Doctors Hospital in Columbus, Ohio from September 2014 through September 2015 with a clinical diagnosis of an acute exacerbation of COPD, defined as an increase in the patient's dyspnea, cough, or change in sputum consistency/volume/color from the patient's baseline during stable conditions. To achieve 80% power to detect a clinically significant difference between study groups, a minimum sample size of 130 patients (65 in each study group) is necessary. To account for issues such as patient study withdrawal and protocol deviations, a sample size of 146 patients (73 per study group) is ideal.

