### *Hypothesis:*

A clinically significant difference exists between albuterol treatments with nebulized 3% saline versus standard saline, for improvements in the patient's modified Borg dyspnea score during an acute exacerbation of COPD.

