#### *Statistical Analysis:*

We will test the hypothesis that a clinically significant difference in dyspnea scores exists between patients who receive hypertonic saline and those who do not. Descriptive statistics will be produced, using means, medians, ranges and standard deviations for continuous variables, and percentages for categorical variables. Independent variables will include modified Borg scores, 30-day mortality and length of hospital stay. Inferential statistics will determine statistically significant differences between comparison variables, using paired sample t-tests or the Wilcoxon signed rank test. Statistical significance will be evaluated at the 5% ( $\alpha=0.05$ ) level.

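### The hypothesis compares two independent randomised arms, but the only tests named are paired ones, with no rule for choosing between them and no use of baseline Borg as a covariate

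*Combined protocol and SAP*

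**What the plan says.** All references are to the combined protocol and SAP.

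- **Hypothesis:** "A clinically significant difference exists between albuterol treatments with nebulized 3% saline versus standard saline", for improvement in the modified Borg score. Statistical Analysis restates this as a contrast between patients who do and do not receive hypertonic saline.
- **Study Population:** the sample size is set to "detect a clinically significant difference between study groups" with 80% power; "a minimum sample size of 130 patients (65 in each study group) is necessary", and "a sample size of 146 patients (73 per study group) is ideal" once withdrawals and deviations are allowed for.
- **Study Design:** patients are randomised to one of two groups. No matching is described. Dyspnea is scored before treatment starts and again after the intervention period.
- **Study Variables:** the data list includes "Modified Borg Scale Score (pre and post treatment").
- **Statistical Analysis:** apart from descriptive summaries and the 5% significance level, the inferential plan is that comparisons will be made "using paired sample t-tests or the Wilcoxon signed rank test". No covariate, regression model or rule for choosing a test is given. The Borg score is called an independent variable, although the hypothesis treats it as the outcome. The plan does not say whether the endpoint is the post-treatment score or the change.

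**The concern.** The question and the tests do not match. A paired t-test or signed-rank test needs each value in one set to have a natural partner in the other. Here the only such partners are the same patient's scores before and after treatment. Applied to those, the tests ask whether dyspnea changed, either within each arm or over both arms together. Patients treated in hospital for an exacerbation may well improve in either arm, so neither result answers the randomised question. Concluding that the arms differ because one reached significance and the other did not is a known route to a false claim.

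Two lesser matters follow. With two tests on offer and no rule, the choice can be made after seeing the results. And if the tests were simply exchanged for their two-sample counterparts, the baseline score, already collected, would still not be used as a covariate.

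**Working it through.** **1. The plan's own figure.** The 130 cannot be reproduced, because no target difference, SD or sidedness is given. Working back with two-sided 5% (assumed, as the hypothesis has no direction) and the stated 80% power:

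d = (1.960 + 0.842) × √(2/65) = 0.491 SD (0.495 with the t distribution).

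In the other direction, an assumed 0.5 SD needs 63 per arm (normal), 64 (t) or 66 to 68 (rank-sum, efficiency 0.955). A paired t-test at 0.5 SD of change would need only 34 pairs in total. So 65 per arm is plausible for a two-group comparison, though this is consistency and not reproduction. With an assumed 10% loss, 65/0.9 = 72.2, rounded up to 73 per arm, which gives 146.

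**2. What the paired tests do when the arms do not differ.** Assume equal SDs before and after, correlation ρ = 0.5, 65 per arm and the same mean improvement in both arms. The SD of change is √(2(1 − 0.5)) = 1 SD. Results from 10,000 simulated trials per row:

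| Improvement in both arms | Exactly one arm significant | Both arms significant | Pooled paired test significant |
|---|---|---|---|
| 0.25 SD | 49.6% | 26.6% | 81.0% |
| 0.30 SD | 44.4% | 44.4% | 92.5% |
| 0.50 SD | 4.4% | 95.6% | 100.0% |
| 1.00 SD | 0.0% | 100.0% | 100.0% |

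Check on the first row: each arm is significant with probability about 0.266 + 0.496/2 = 0.514, and 2 × 0.514 × 0.486 = 0.50. The one-arm-only pattern depends strongly on how much patients improve. In every row the tests reflect improvement over time and carry no information on the arm difference.

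**3. What ANCOVA would add over an unadjusted two-group test.** With equal SDs and a common slope, the variance of the treatment effect under ANCOVA, relative to the alternative, is:

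- against change scores: (1 − ρ²) / [2(1 − ρ)] = (1 + ρ)/2
- against post scores: 1 − ρ²

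If the unadjusted test has 80% power at 65 per arm, ANCOVA power = Φ(2.802/√ratio − 1.960). For example, at ρ = 0.5 the ratio is 0.75 either way: 2.802/0.866 − 1.960 = 1.275, and Φ(1.275) = 89.9%.

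| Assumed ρ | Ratio to change | ANCOVA power | Ratio to post | ANCOVA power |
|---|---|---|---|---|
| 0 | 0.50 | 97.7% | 1.00 | 80.0% |
| 0.2 | 0.60 | 95.1% | 0.96 | 81.6% |
| 0.3 | 0.65 | 93.5% | 0.91 | 83.6% |
| 0.5 | 0.75 | 89.9% | 0.75 | 89.9% |
| 0.7 | 0.85 | 86.0% | 0.51 | 97.5% |
| 0.8 | 0.90 | 84.0% | 0.36 | 99.7% |

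The two power columns rest on different premises (65 per arm sized on change, or on post scores). The plan does not say which applies.

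**4. Open choice of test.** The named tests do not compare arms, so their two-sample counterparts were simulated: 5,000 null trials, 65 per arm, normal data. Type I error was 4.9% for the t-test, 5.0% for the rank-sum test, and 5.8% when the smaller p-value was taken.

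**The case against.** The best defence is that the word paired is a slip. The hypothesis and the sample size both speak of a difference between groups, and 65 per arm fits a two-sample calculation, so the trial team may well intend two-sample tests. That is a fair reading of intent. It does not repair the text: the named tests are those an analyst following the plan would run, and a two-sample substitute would still leave the endpoint, the covariate and the choice of test open.

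A reader might infer that the planned between-arm comparison wastes power or is underpowered. The documents do not support this. No between-arm test is specified whose power could be lost. If 65 per arm does give an unadjusted test 80%, the stated target is met and ANCOVA adds to it. A reader might also infer that the open choice of test costs power; taking the smaller p-value does the opposite, since it rejects slightly too often. Nor is baseline simply ignored: a paired pre/post test uses it, but not as a covariate and not to compare arms.

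It is also tempting to argue that broad entry criteria make baseline Borg vary widely and so make adjustment worthwhile. No data on spread are given, and by the formulas above the gain depends on ρ.

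Finally, the repair needs more than a change of test name. Exclusion Criteria removes patients found after enrolment to have another main cause, which bears on who is analysed. The treatment period has a minimum length but no fixed end, so the time of the post-treatment score is not fixed either. Both points stand and are taken up in the fix.

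**Conclusion.** The point holds as a mismatch between hypothesis and test: as written, the plan has no valid analysis of its own between-arm hypothesis. This follows from the text alone and needs no assumption beyond independent, unmatched arms.

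The efficiency benefit is secondary and conditional. Over ρ = 0.3 to 0.7 it is about 6 to 14 percentage points of power against a change-score test (86.0% to 93.5%, from 80%) and about 4 to 18 against a post-score test (83.6% to 97.5%). Against post scores it shrinks to nothing at ρ = 0. These figures assume equal variances, a common slope and 80% power for the unadjusted test; none of these can be checked from the documents. The error from choosing between tests after the fact is small, at roughly one percentage point.

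**What to change.** In Statistical Analysis:

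1. Replace the paired tests, for the primary comparison, with one prespecified between-arm analysis: ANCOVA of the post-treatment Borg score on treatment group with baseline Borg as covariate. Report the adjusted mean difference with its 95% CI, tested at two-sided 5%.
2. Name one sensitivity analysis, rank-based or proportional-odds, also adjusted for baseline. Describe the Borg score as the outcome.
3. State the analysis population and reconcile it with the post-enrolment exclusion in Exclusion Criteria. Define which post-treatment score is analysed and how missing scores are handled.
4. In Study Population, state the difference, SD, sidedness and loss rate behind 130 and 146, and the pre/post correlation if the calculation relied on one.

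Paired tests may remain as descriptive summaries of change within each arm.

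The cost is a short paragraph. Both scores are already collected, so no extra patients or measurements are needed. The analysis population and the timing of the score call for a decision by the study team as well as an edit.

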#### *Statistical Analysis:*

We will test the hypothesis that a clinically significant difference in dyspnea scores exists between patients who receive hypertonic saline and those who do not. Descriptive statistics will be produced, using means, medians, ranges and standard deviations for continuous variables, and percentages for categorical variables. Independent variables will include modified Borg scores, 30-day mortality and length of hospital stay. Inferential statistics will determine statistically significant differences between comparison variables, using paired sample t-tests or the Wilcoxon signed rank test. Statistical significance will be evaluated at the 5% ( $\alpha=0.05$ ) level.

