### Inclusion Criteria:

- Patients at least 18 years of age
- Admitted to Doctors Hospital with a clinical diagnosis of COPD within 24 hours.

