### Exclusion Criteria:

- Patients younger than 18 years of age
- History of smoking less than twenty pack-years
- Possibility of other primary cause of the patient's change in dyspnea or cough (e.g. pneumonia, congestive heart failure with pulmonary edema, myocardial infarction)
- Patient is found to have a different primary cause after initial enrollment
- Patients admitted over 24 hours prior to contact by study staff/investigator
- Non-English speaking subjects

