### *Study Design:*

This randomized, single-blind, prospective study will involve 146 patients admitted to Doctors Hospital with a clinical diagnosis of an acute exacerbation of COPD. Patients will be randomly assigned to 2.5 mg albuterol treatments with either normal saline, as is the standard, or hypertonic saline. The Doctors Hospital biostatistician will create a randomization plan that will be kept with the consent forms. The investigator or study staff will maintain the list and determine the study treatment by subject number.

Once the patient has been identified by the inclusion/exclusion criteria, they will be approached by a study staff member and informed of the opportunity to participate in the study. The study staff will then provide a detailed explanation of the study and obtain patient consent.

Once the patient is enrolled, they will receive the 2.5mg albuterol treatment, and saline solution as determined by the randomization plan (Group 1 will receive 0.9% saline and Group 2 will receive 3% saline), every six hours for at least the first 24 hours, with allowance for PRN (*pro re nata*= as needed) use every four hours by patient request. The nebulized saline will be kept in the pharmacy and will be ordered in the same way as the standard saline. The patient's dyspnea will be evaluated prior to starting the treatment and after the intervention period is completed using the Modified Borg Dyspnea Scale. The scale will be administered by either the investigator or study staff.

Participation in the study will be complete once the patient is discharged from the hospital. All patients will be recommended to have spirometry or full pulmonary function testing as an outpatient once stable, if not already obtained.

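### Length of hospital stay is named for analysis but neither listed for collection nor defined, and as raw days it would score an early in-hospital death as a short stay

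*Combined protocol and SAP*

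**What the plan says.** The Statistical Analysis section names what will be analysed: "Independent variables will include modified Borg scores, 30-day mortality and length of hospital stay". It calls these independent variables, although they act as outcomes. The tests are to be run "using paired sample t-tests or the Wilcoxon signed rank test".

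The Study Variables section opens with "The data to be collected from this study will include" and gives seven items: demographics, treatment group, Borg score before and after treatment, as-needed albuterol use, 30-day readmission, 30-day mortality and spirometry. Length of stay is not among them. Nor is a date or time of admission, randomisation, first study treatment, discharge or death, or a discharge status. Death appears only as "30 day all cause mortality".

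The sequence of events comes from three other sections:

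- Inclusion Criteria: "Admitted to Doctors Hospital with a clinical diagnosis of COPD within 24 hours".
- Exclusion Criteria, which rule out: "Patients admitted over 24 hours prior to contact by study staff/investigator".
- Study Design, which starts treatment after enrolment ("Once the patient is enrolled, they will receive the 2.5mg albuterol treatment") and sets the end of follow-up: "Participation in the study will be complete once the patient is discharged from the hospital".

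**The concern.** A variable is named for analysis with no listed source, no start, no end and no rule for patients who die before discharge. An analyst would probably take the hospital's own count of days. On that count a patient who dies on day 2 contributes 2 days, which reads as a better result than a survivor who goes home on day 5. If early deaths are more frequent in one arm, that arm's stay looks shorter for the wrong reason. The listed data could not reveal this, because 30-day mortality without date or place does not separate a death in hospital from one after discharge. With no rule in the plan, the handling of deaths could also be chosen after the data are seen.

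**Working it through.** **The two lists side by side**

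| Named for analysis | In the collection list? |
|---|---|
| Modified Borg score | Yes, before and after treatment |
| 30-day mortality | Yes, without date or place of death |
| Length of hospital stay | No, and no dates from which to derive it |

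The plan has no figure for length of stay to reproduce. The sample size (130, raised to 146) is tied to the dyspnea hypothesis and does not bear on this point. The only input taken from the plan is 73 patients per group. Stay lengths, death rates and standard deviations below are assumptions.

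**Step 1: effect of early deaths on a raw mean stay**

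Shift in the arm's mean = (k / 73) × (S − D), where k is the number of excess early deaths, S the stay otherwise expected and D the day of death.

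- k = 2, S = 5, D = 2: 2/73 × 3 = 0.08 day.
- k = 4, S = 8, D = 2: 4/73 × 6 = 0.33 day.

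A second set of assumptions uses in-hospital death rates m0 and m1, with a survivor mean of 5 days. Shift = (m1 − m0) × (5 − D).

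| Mortality by arm | Expected deaths per 73 | Death on day 2 | Death on day 1 |
|---|---|---|---|
| 2% and 2% | 1.5 and 1.5 | 0 | 0 |
| 2% and 5% | 1.5 and 3.7 | 0.09 day | 0.12 day |
| 5% and 10% | 3.7 and 7.3 | 0.15 day | 0.20 day |

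In each non-zero row the arm with more deaths looks better. The sign depends on D being smaller than S: a patient who dies after a long admission scores a long stay.

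**Step 2: time between admission and randomisation**

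Suppose the gap is uniform over 0 to 24 hours. Its variance is 1/12 = 0.083 day². Patients per group to detect a 1-day difference (two-sided 5%, 80% power) are n = 2 × (1.960 + 0.842)² × SD², about 15.70 × SD². Adding 0.083 to SD² gives:

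| SD after randomisation (days) | n without gap | n, uniform gap | n, gap of 0 or 24 h (half each) |
|---|---|---|---|
| 2 | 63 | 65 | 67 |
| 3 | 142 | 143 | 146 |
| 4 | 252 | 253 | 256 |

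The gap costs 1 to 4 patients per group in precision. It arises before allocation, so its expected difference between arms is zero.

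**Step 3: the named tests**

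Both named tests work on pairs. A stay has one value per patient and the arms are independent, so neither test can compare stay between arms.

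**The case against.** The strongest reply is that this is a missing line on a list. The wording of the collection list is open, so leaving out length of stay does not exclude it. A reader might infer that the two sections contradict each other; they do not, and what stands is an omission. A reader might also infer that the outcome cannot be recovered. That goes too far: admission time must be known to apply the 24-hour limit, discharge ends participation, and both should be in the hospital record.

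Two further inferences are tempting. One is that time before study treatment biases the comparison. It does not, because it precedes allocation; step 2 shows only slight noise. The other is that raw days always flatter the arm with more deaths. That holds only for early deaths that differ between arms. A large excess of deaths would also show in 30-day mortality, which is collected and analysed.

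Finally, the hypothesis concerns the Borg score alone, so length of stay cannot change the trial's main conclusion. All of this stands and limits the weight of the point. It does not supply a definition or a rule for deaths. An analyst given only the words length of hospital stay would not necessarily handle deaths in the way proposed below.

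**Conclusion.** The point holds as a gap in listing and definition, with a modest possible distortion. The plan names length of stay for analysis, does not list it or the items needed to derive it, and has no rule for in-hospital deaths. As raw days, the measure can favour the arm with more early deaths by about 0.1 to 0.3 day. That range assumes 2 to 4 excess early deaths in 73, death on day 2 and an otherwise expected stay of 5 to 8 days. The documents support none of these values directly, and the shift is zero if early mortality is equal. The documents do not support a finding of contradiction between sections, of bias from time before randomisation, or of any effect on the dyspnea hypothesis. The change is worth making because it is cheap and fixes the rule for deaths before data are seen.

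**What to change.** In Study Variables, add the date and time of admission, of randomisation, and of discharge or in-hospital death, together with discharge status (alive or dead).

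In Statistical Analysis, define length of stay as a secondary outcome: time from randomisation to discharge alive, with every in-hospital death ranked as the worst (longest) value. Compare the two independent arms with a Wilcoxon rank-sum test instead of a paired test. Treating death as a competing event is a workable alternative; whichever is chosen should be written down in advance. If the sponsor does not want this outcome, deleting it from the analysis section also removes the mismatch.

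The cost is a few chart items and a short definition. The result becomes a median or rank comparison instead of a mean number of days, though the plan already intends to report medians. Neither the study treatment nor the sample size changes.

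### The hypothesis compares two independent randomized groups, but the only tests named are paired, so the plan names no test of it

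*Combined protocol and SAP*

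**What the plan says.** The protocol states a between-group question in three places.

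- Hypothesis: "A clinically significant difference exists between albuterol treatments with nebulized 3% saline versus standard saline, for improvements in the patient's modified Borg dyspnea score".
- Statistical Analysis: the aim is to test whether a "clinically significant difference in dyspnea scores exists between patients who receive hypertonic saline and those who do not".
- Study Population: the sample size is set "To achieve 80% power to detect a clinically significant difference between study groups", with at least 65 patients in each.

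Study Design describes a parallel-group trial: "Group 1 will receive 0.9% saline and Group 2 will receive 3% saline". It mentions no crossover and no matching of patients.

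The only inferential methods named anywhere are in Statistical Analysis: "Inferential statistics will determine statistically significant differences between comparison variables, using paired sample t-tests or the Wilcoxon signed rank test". Just before that, the section lists what is to be analyzed: "Independent variables will include modified Borg scores, 30-day mortality and length of hospital stay". Study Variables lists the Borg score before and after treatment, so the only natural pairs in the data are the two scores from one patient.

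**The concern.** A paired t-test or signed rank test needs two linked observations. Applied to the two Borg scores of each patient, it asks whether the mean or median change differs from zero. That is a question about change over time, and the answer can be yes whether or not hypertonic saline adds anything. Every patient receives albuterol while in hospital for an acute exacerbation, so improvement in both groups is plausible.

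If the sentence is followed as written, the randomized comparison is never made. A significant paired result could be taken as evidence for the treatment when it shows only that patients got better. Conversely, if both groups improve clearly, both paired tests are significant and a real difference between groups goes unseen. The other two listed outcomes have no pair at all, and no method for a binary outcome is named.

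**Working it through.** **1. Do the named tests fit the outcomes?**

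| Outcome | Values per patient | Paired test across groups? | Paired test within patient? |
|---|---|---|---|
| Borg score | two (pre, post) | no, patients are not matched | yes, but it tests improvement over time |
| Length of stay | one | no | no |
| 30-day mortality | one, binary | no | no |

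No cell gives a test of the stated hypothesis.

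**2. The plan's own figure.** The minimum of 130 patients (65 per group) for 80% power cannot be reproduced, because no effect size, SD or test is given. Assume a difference of 0.5 SD and two-sided alpha of 0.05. The normal approximation gives n per group = 2 × (1.960 + 0.842)² / 0.5² = 62.8, so 63; the two-sample t-test needs 64. Conversely, 65 per group gives 80% power for 0.495 SD. The stated size is thus compatible with a two-group test.

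**3. What the paired tests would show.** Inputs from the plan are 65 per group and alpha 0.05. Assumptions are a two-sided test (the hypothesis is non-directional), normally distributed change with SD 1, and a range of mean improvement *m* in SD units. Let q(m) be the power of a paired t-test in one group, from the noncentral t with 64 df and noncentrality m√65.

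- No treatment effect, exactly one group significant: 2q(1 − q).
- No treatment effect, one paired test on all 130 patients: same power formula with n = 130.
- True effect of 0.495 SD, hypertonic group significant and normal saline group not: q(m + 0.495) × (1 − q(m)), where *m* is the improvement in the normal saline group.

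| Improvement *m* (SD) | q(m), n = 65 | No effect: groups disagree | No effect: pooled test significant | True effect: hypertonic only |
|---|---|---|---|---|
| 0 | 0.050 | 9.5% | 5% | 93% |
| 0.2 | 0.355 | 46% | 62% | 64% |
| 0.25 | 0.510 | 50% | 81% | 49% |
| 0.35 | 0.794 | 33% | 98% | 21% |
| 0.5 | 0.978 | 4% | >99.9% | 2% |
| 0.75 | >0.999 | about 0% | >99.9% | about 0% |

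Example at *m* = 0.2: 2 × 0.355 × 0.645 = 0.458, or 46%. The disagreement column cannot exceed 50%, which it reaches at q = 0.5.

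A two-sample t-test on change does not depend on *m*: it rejects in 5% of trials under no effect and has 80% power at 0.495 SD. Simulation with 20,000 trials per case agreed: disagreement of 45.8%, 50.2%, 32.9% and 4.4% at 0.2, 0.25, 0.35 and 0.5 SD, and a two-sample error rate of 4.9% to 5.1%.

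**The case against.** The strongest reply is that this is a slip of wording. The hypothesis, the power statement and the aim all speak of groups, and the section is loose elsewhere (it labels outcomes as independent variables). A competent analyst would probably substitute a two-sample test, especially as a paired test cannot be run on mortality. That is a fair reading of intent, but it does not remove the defect. The substitution would be an unrecorded departure from the plan, and the choice of test would stay open until the data are seen.

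A second reply is that paired tests are legitimate for pre/post Borg scores. They are, as a description of change within a group, but that still leaves the hypothesis without a test.

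A third objection, which stands, is that the percentages do not measure this plan. Judging by which group is significant, and pooling all 130 patients, are both uses that the plan does not state. The highest disagreement occurs only near 0.2 to 0.25 SD of common improvement. The 80% power of the two-sample test follows from choosing 0.495 SD as the effect. The figures illustrate the risk, and the finding does not depend on them.

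It is also fair that ANCOVA is a preference and not a necessity, and that the adequacy of 65 per group cannot be verified. If an assumed 0.5 SD effect is on the post-score scale, the requirement at pre/post correlations of 0.3 to 0.7 runs from 88 down to 38 per group for change scores, and from 58 down to 33 for ANCOVA.

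**Conclusion.** The concern holds, and the text must be corrected before analysis. The mismatch between a between-group hypothesis and paired tests follows from the text alone, with no numerical assumption. The one sentence that says how the hypothesis will be tested gives the wrong analysis if followed, and nothing elsewhere in the document supplies another.

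The size of the consequence depends on how much patients improve and on how the paired results would be read, neither of which the plan states. Under the assumptions above, false disagreement between groups ranges from about 0% to 50%. The chance that a true 0.495 SD effect shows as significance in the hypertonic group alone falls from 93% to about 0% as improvement on normal saline rises from 0 to 0.75 SD.

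Two related points are minor: the outcomes are labeled independent variables, and length of stay is to be analyzed but is not in the Study Variables list.

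**What to change.** Replace the test sentence in Statistical Analysis with text such as:

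> The primary analysis compares the post-treatment modified Borg score between treatment groups by ANCOVA with the pre-treatment score as covariate, and reports the adjusted difference with its 95% CI. A Wilcoxon rank-sum test on change from pre- to post-treatment is the sensitivity analysis. Length of stay is compared by Wilcoxon rank-sum test. Thirty-day mortality is compared by Fisher exact test, with risk difference and 95% CI. Paired tests are used only to describe change within each group.

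The minimum repair is a two-sample t-test or rank-sum test on Borg change. ANCOVA is preferred because the pre-treatment score is already collected. A chi-square test would also serve for mortality, but one test should be fixed in advance. If readmission and as-needed albuterol use are to be compared, their tests should be named too.

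Label treatment group as the independent variable and the outcomes as dependent variables, and add length of stay to Study Variables.

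The cost is analysis text and one data item. Borg scores, treatment group and 30-day mortality are already listed for collection, although Study Design ends participation at discharge and does not say how later deaths will be found. Changing the test does not itself require more patients; whether 65 per group is enough cannot be judged until the effect size and SD are stated.
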